## **Estimated sample size**

This pilot study will be time driven, as the pre-specified time limit for data collection is two months. The minimum recruited number of participants required for each study group will be 30 patients, giving a minimum number of 60 patients in total. However, the research team strived to recruit as many patients as possible during those two months. This is to determine the actual treatment effect size, and the participant recruitment and retention rates to be used in the sample size calculation for the main evaluation trial.

A prior study has been conducted at the same primary healthcare centre that this pilot study will be performed, assessing outpatient management of dengue illness. This prior study hads a default rate of 16.4% amongst the outpatient suspected dengue cases, which was approximately half of the average default rate of patients attending the general outpatient clinic at University Hospital (33.8%) . However, the current default rate for suspected dengue patients at the primary healthcare clinic might have changed since then.

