# Study design

This is a single centre, unblinded, parallel-group study with balanced randomisation (1:1 ratio) for the two groups of patients.

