## Randomization

## Method of sequence generation

A table of random numbers will be used.

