## Type of randomization

Simple randomisation will be done, with a 1:1 allocation ratio. Participants are supposed to be distributed equally between the two study groups.

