#### Implementation of the random sequence

Once consent is obtained, either the researcher or the trained research assistant will then allocate the patient into either one of two groups: the control group or the intervention group. This will be done using the table of random numbers. If the patient gets an odd number, they will be allocated to the control group, if the patient gets an even number, they will then be allocated to the intervention group.

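### A total of 60 is paired with at least 30 per group, but simple randomisation of 60 patients gives 30 in both groups only about 10% of the time

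*Protocol*

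**What the plan says.** Four parts of the Protocol bear on this point.

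- **Estimated sample size** sets the target: "The minimum recruited number of participants required for each study group will be 30 patients, giving a minimum number of 60 patients in total". The same section says that the study runs for a fixed two months and that the team aims to recruit as many patients as it can in that time. It gives no upper limit and no projected number.
- **Type of randomization** names the method and the expected result: "Simple randomisation will be done, with a 1:1 allocation ratio. Participants are supposed to be distributed equally between the two study groups".
- **Method of sequence generation** and **Implementation of the random sequence** give the mechanism. The first says: "A table of random numbers will be used". The second says: "If the patient gets an odd number, they will be allocated to the control group"; an even number leads to the intervention group. No block, stratum or other restriction is described.
- **Study design** describes a "parallel-group study with balanced randomisation (1:1 ratio) for the two groups of patients".

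**The concern.** Drawing an odd or even number for each patient is a separate 50:50 draw. Nothing in it pulls the two groups back towards equal size, so the group sizes are themselves random. A minimum of 30 in each group therefore does not follow from a minimum of 60 in total: at 60, any split other than 30:30 leaves one group short. The Protocol makes no allowance for this, and it states an expectation of equal groups that the method does not secure.

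What is at stake is the pilot's own recruitment minimum. The Study objectives section lists randomisation of participants among the processes whose feasibility is being tested, and the pilot is meant to supply the effect size and sample size for the main trial. The stated minimum should be one that the stated method can be expected to deliver.

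**Working it through.** **Inputs, all from the Protocol.** Minimum per group 30 and minimum total 60 (Estimated sample size). Simple randomisation at 1:1 (Type of randomization). Odd to control and even to intervention, from a random number table (Implementation of the random sequence; Method of sequence generation). Odd and even digits are equally frequent in such a table, so each patient has probability 0.5 of either group, independently of the others.

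**The plan's own figure.** 2 × 30 = 60. This reproduces. No significance level, power, effect size or standard deviation is given behind the 30, so there is no sample size formula to check.

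**Chance of at least 30 in both groups.** Let X be the number in one group, X ~ Binomial(N, 0.5). Then

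P(both groups ≥ 30) = Σ C(N, x) / 2^N, for x = 30 to N − 30.

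At N = 60 the sum has one term, x = 30:

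P = C(60, 30) / 2^60 = 0.1026.

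So if recruitment ended at 60, one group would fall below 30 with probability 1 − 0.1026 = 0.897.

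**How far short at N = 60.**

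- Expected absolute difference between groups: 6.15.
- Expected smaller group: (60 − 6.15) / 2 = 26.9.
- P(both groups ≥ 27) = 0.634, so P(smaller group ≤ 26) = 0.366.
- P(both groups ≥ 25) = 0.845, so P(smaller group ≤ 24) = 0.155.

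**How the chance changes with the total recruited.**

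| Total N | P(both groups ≥ 30) |
|---|---|
| 60 | 0.103 |
| 65 | 0.543 |
| 70 | 0.812 |
| 74 | 0.919 |
| 76 | 0.9495 |
| 77 | 0.960 |
| 80 | 0.982 |
| 83 | 0.992 |

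The first total to reach 90% is 74, and the first to reach 95% is 77; 76 falls just short.

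**Cost in precision.** For a comparison of two means with equal variances, a split a:b has efficiency 4ab / (a + b)² relative to equal groups.

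- 26:34 gives 4 × 26 × 34 / 3600 = 0.982.
- 24:36 gives 4 × 24 × 36 / 3600 = 0.960.
- 22:38 gives 4 × 22 × 38 / 3600 = 0.929.

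The probability that both groups have at least 22 is 0.973, so a loss much above 7% would be unusual.

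**The case against.** The strongest reply is that 60 is a floor and not a planned total. Recruitment is time driven, the team means to exceed the minimum, and 60 is correctly the smallest total at which 30 per group is possible. This stands, and it limits the point: the 10.3% applies only if recruitment ends at exactly 60. A reader might infer that the trial has only a one in ten chance of meeting its minimum. The Protocol does not support that, because it neither stops at 60 nor projects how many patients two months will bring. For the same reason it gives no assurance that the total will be well above 60.

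A reader might also infer that the Study design section contradicts the choice of simple randomisation. It does not clearly do so. The phrase "parallel-group study with balanced randomisation (1:1 ratio" can mean only that the allocation ratio is equal, which simple 1:1 randomisation satisfies. The explicit expectation of equal groups is in the Type of randomization section: "Participants are supposed to be distributed equally between the two study groups".

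A third inference would be that season or sex will drift between the groups. Nothing in the Protocol supports this. Recruitment lasts two months, the Protocol does not discuss season as a confounder, and unequal group size is a different matter from covariate imbalance. Unstratified blocks would not specifically balance sex either.

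Finally, simple randomisation is a legitimate method and its unpredictability is an advantage in an open trial. No power target, stopping rule or analysis is tied to 30 per group, so a group of 27 would invalidate nothing. Both remarks are fair. What remains is that the stated total, the stated per-group minimum and the stated method do not fit together.

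**Conclusion.** The point holds as a modest inconsistency between stated size and stated method. At the stated minimum total, simple randomisation meets the stated per-group minimum 10.3% of the time, with an expected smaller group of about 27. The chance rises to 81% at 70 patients, 92% at 74, 96% at 77 and 98% at 80. The typical loss of precision is a few per cent, so validity is not threatened.

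The figures assume independent draws with probability 0.5 and count patients as recruited, which is how the Protocol defines the minimum. The 16.4% default rate that the Protocol cites from a prior study at the same centre is not applied here. Where the real probability falls depends on the number recruited in two months, which the Protocol does not project.

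**What to change.** Choose one of two changes before recruitment starts.

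1. **Restrict the randomisation.** Use randomly permuted blocks of mixed size, for example 4 and 6, from a list prepared in advance and concealed from those who recruit. Both sizes are even, so at 60 patients an unfinished block holds 2 or 4 patients and the groups differ by at most 2: the worst split is 29:31. At 62 patients the worst split is 30:32, so both groups have at least 30. The cost is a new list and a short change to the randomisation sections. The drawback is that blocks are partly predictable in an open trial, so this option needs concealment, and the Allocation concealment section, which now says that none is used, would have to change with it.

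2. **Keep simple randomisation.** Restate the minimum total as about 77 for 95% assurance of at least 30 per group, or 74 for 90%, and delete the sentence expecting equal groups. The cost is 17 or 14 more patients on the stated minimum (77 − 60 or 74 − 60), which the fixed two months may or may not provide.

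Under either option, make the Type of randomization and Estimated sample size sections agree. It would also help to say in the Study design section that balanced refers to the allocation ratio, if that is what is meant.

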# Study objectives

- 1. To determine the feasibility of the designed research process in terms of the following:
  - a. Recruitment/retention of participants
  - b. Randomisation of the participants.
  - c. Logistics manpower, resources
- 2. To determine the feasibility and acceptability of the designed intervention in terms of the following:
  - a. Usage of the cups as a standardized measure of fluid intake
  - b. Usage of the fluid charts as a tool for behaviour change
  - c. The implementation process of the intervention
- 3. To determine the trend of the preliminary results in order to:
  - a. To estimate the treatment effect size of the experimental intervention
  - b. To calculate the sample size for the main evaluation randomized controlled trial.
- 4. To refine the research process and intervention design for the main evaluation randomized controlled trial.

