# **Statistical analysis**

All the data for this pilot study will be expressed either as the mean  $\pm$  standard deviation or as frequencies and proportions. Differences in data between the control and intervention group will be analysed using the Student's t test for continuous variables. The chi-squared test ( $\chi^2$  test) or the Fisher's exact test will be used for categorical variables, whichever is appropriate. A p value < 0.05 is considered as statistically significant. The statistical software utilised for the analysis is SPSS version 16.0 (SPSS Inc. Cary, NC).

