## Defaulted follow-up and drop out

The term defaulted follow-up means that the patient comes to see the researcher at least once after recruitment into the study. This is not interchangeable with the term drop out, meaning the patient is only seen once by the researcher or the assistants during recruitment, and does not return to see the research team at all after recruitment.

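### The pilot's effect estimate is too imprecise to be the main trial's design effect, and the default and drop-out definitions need correcting before they supply a retention rate

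*Protocol*

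**What the plan says.** Under Estimated sample size the pilot is time-driven. It sets a floor, "The minimum recruited number of participants required for each study group will be 30 patients, giving a minimum number of 60 patients in total", and adds "However, the research team strived to recruit as many patients as possible during those two months". The reason, which concerns planning of the main trial, follows directly: "This is to determine the actual treatment effect size, and the participant recruitment and retention rates to be used in the sample size calculation". Preliminary outcome measures also speaks of determining the effect size. Study objectives is more cautious, "To estimate the treatment effect size of the experimental intervention", as are the primary questions that close the Background, and both describe the results as a preliminary trend. Statistical analysis plans means with standard deviations, proportions, group tests and "A p value < 0.05 is considered as statistically significant". It names no confidence interval.

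The section Defaulted follow-up and drop out defines two terms that it says are not interchangeable. For the first: "The term defaulted follow-up means that the patient comes to see the researcher at least once after recruitment into the study". A drop-out is a patient seen once, at recruitment, who "does not return to see the research team at all after recruitment". No exception is made for admission. Defaulter tracing, by contrast, expects that some patients will miss follow-up because they are in hospital, and has the hospital, date, reason and source of the recommendation recorded.

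**The concern.** The effect size, the retention rate and the main-trial sample size are stated products of this pilot (Study objectives 1a, 3a and 3b; Outcomes 4).

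- **Effect size.** A pilot of this order does not determine an actual effect. It gives an estimate with a wide interval. If the point estimate becomes the design effect, a chance-high value yields an underpowered main trial. A chance-low value yields a needlessly large one or a decision not to proceed.
- **Retention.** As worded, a defaulter is anyone who came back at least once, so no default rate can be computed from the text that is comparable with the 16.4% cited from the earlier study at this clinic. Drop-out, as worded, counts as lost some patients whose hospitalisation outcome is known. A main trial powered on hospitalisation and inflated by that rate would recruit too many.

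**Working it through.** **1. The plan's own figure.** 2 × 30 = 60, which agrees. No effect size, SD, event rate, power or precision target stands behind the 30, so no formula can reproduce it.

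**2. Precision of a difference in hospitalisation.** The 95% half-width with n per group and a common rate p is 1.96 × √(2p(1−p)/n). I take p = 0.50. This is an assumption: Study setting gives 40% to 63.41% for suspected cases at the clinic, but patients needing admission at the first visit are excluded, so the rate among recruits is not given. Equal groups are also assumed; the plan says "Simple randomisation will be done, with a 1:1 allocation ratio", so some imbalance is possible.

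| n per group | Half-width |
|---|---|
| 30 | 1.96 × √(0.50/30) = 0.253 |
| 60 | 1.96 × √(0.50/60) = 0.179 |
| 100 | 1.96 × √(0.50/100) = 0.139 |

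The rate matters little: at 30 per group the half-width is 0.248 for p = 0.40 and 0.244 for p = 0.634. For a continuous outcome with an assumed standardised difference of 0.5, it is 1.96 × √(2/30 + 0.25/120) = 0.51 SD.

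**3. What follows if the point estimate sizes the main trial.** The document states no true rates, so I assume 50% v 35%, two-sided 0.05 and 80% power. The size needed is (1.96 + 0.8416)² × (0.50 × 0.50 + 0.35 × 0.65)/0.15² = 7.849 × 0.4775/0.0225 = 166.6, that is 167 per arm. In 200,000 simulated pilots per row, each planned from its own observed rates:

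| Pilot n per group | No benefit or harm observed | Plan made, true power under 50% | Planned n per arm, 10th to 90th percentile |
|---|---|---|---|
| 30 | 14% to 15% | 30% | 32 to 876 |
| 60 | 6% | 26% | 51 to 1,409 |
| 100 | 2% | 18% | 63 to 788 |

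The second and third columns are shares of all pilots. The last column covers only pilots that observed a benefit. At 100 per group, about half of those plans still fall below 80% true power. An assumed 40% v 25% gives much the same picture (13% and 30% at 30 per group).

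**4. The two definitions beside the tracing rule.**

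| Patient | Label as written | Hospitalisation known? |
|---|---|---|
| Returns to every visit | Meets the wording for defaulted follow-up | Yes |
| Returns once, then misses a visit | Defaulted follow-up | Depends on tracing |
| Admitted before any return, never seen again by the team | Drop-out | Yes, if tracing succeeds |
| Never returns and cannot be reached | Drop-out | No |

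The first and third rows are the faults.

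**5. Illustration of the retention error.** Let a be the share admitted before a second contact, none of whom returns to the team, with the admission known. Let 16.4% of the rest be lost. Both are assumptions. With a = 0.10:

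- true loss for hospitalisation: 0.90 × 0.164 = 0.148;
- drop-out as defined: 0.10 + 0.148 = 0.248;
- inflation factors: 1/(1 − 0.148) = 1.17 and 1/(1 − 0.248) = 1.33;
- ratio: 1.33/1.17 = 1.13, about 13% too many patients.

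**The case against.** Several points on the other side stand.

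- Thirty per group is a floor in a pilot that recruits all it can in two months, so ±25 points is the least favourable case unless a group falls short of the minimum.
- A reader might infer that both inputs will be wrong. The documents do not support that. The effect estimate is imprecise, not thereby biased. The protocol gives no formula for retention, so that rate is wrong only if the definitions are applied as written.
- Nothing says that the bare point estimate will be used without allowance for its uncertainty. Other sections already use the verb estimate, and confidence intervals may be in an analysis plan that is not shown.
- A reader might infer that every adherent patient will be recorded as a defaulter. Defaulter tracing uses the word in its ordinary sense, so the missing clause is evidently a drafting omission.
- The drop-out rate as defined is a fair loss rate for fluid intake and for the haematocrit and platelet differences between consultations 1 and 2. A patient never seen again generally has no such values, admitted or not. Counting admitted patients as retained for every outcome would overstate retention.
- With 40% admitted before a second contact, the sum in step 5 would give an excess near 80%. The document does not support that share. The clinic's 40% to 63.41% covers all suspected cases, first-visit admissions are excluded, and patients admitted after one return visit are not drop-outs. The 16.4% is itself a default rate whose definition is not given.

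A larger pilot does not remove the effect-size problem, as the 60 and 100 rows show. The drafting omission still leaves an operative definition that cannot yield the intended rate.

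**Conclusion.** The point holds in a limited form. Recruiting to determine an actual effect claims more than the pilot can give: the 95% half-width for hospitalisation is about 25 points at the stated minimum, 18 at 60 and 14 at 100 per group, assuming a rate near 50% and equal groups. A main trial sized on the point estimate could be badly under- or over-sized. How badly depends on true rates that the document does not state.

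The default definition omits the missed visit. The drop-out definition misclassifies admitted non-returners for hospitalisation, and for intravenous fluid, which the protocol assumes from admission. The size of the retention error cannot be fixed from the document, because the share admitted before a second contact is not given. The 13% excess is an illustration resting on the assumed 10% and 16.4%.

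These are corrections to stated rules that feed the pilot's main products. They should be made, but they do not show that the pilot fails.

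**What to change.** 1. In Preliminary outcome measures and Estimated sample size, replace the wording about determining the (actual) effect size with estimating it, with a 95% confidence interval. State that the main trial will be sized on a justified important difference, taking only the control event rate, the SDs and retention from the pilot.
2. Define defaulted follow-up as: returned at least once after recruitment, then missed a later scheduled visit and was not retrieved.
3. Report retention by outcome. Patients with known admission status count as retained for hospitalisation and for intravenous fluid. Patients with no follow-up contact count as lost for fluid intake and for the consultation 2 minus 1 haematocrit and platelet differences, unless those values are obtained.

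The cost is a few sentences and slightly more reporting. The main-trial size may come out larger than an optimistic pilot estimate would give.

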# **Statistical analysis**

All the data for this pilot study will be expressed either as the mean  $\pm$  standard deviation or as frequencies and proportions. Differences in data between the control and intervention group will be analysed using the Student's t test for continuous variables. The chi-squared test ( $\chi^2$  test) or the Fisher's exact test will be used for categorical variables, whichever is appropriate. A p value < 0.05 is considered as statistically significant. The statistical software utilised for the analysis is SPSS version 16.0 (SPSS Inc. Cary, NC).

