#### Allocation concealment

No concealment of allocation will be employed.

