## Preliminary outcome measures

The outcomes will be assessed at the end of the two month period of data collection.

Several preliminary outcomes measures will be used to assess the trend of the preliminary results in order to determine the treatment effect size of the fluid chart. The two pilot study groups will be compared in terms of:

- 1. The hospitalization rates
- 2. The need for intravenous fluid treatment
- 3. The severity of haemoconcentration. Four surrogate endpoints were utilized to determine this, and they were as follows:
  - a. The mean peak haematocrit
  - b. The difference in haematocrit level between the values of clinic consultation 2 clinic consultation 1.
  - c. Those above the local cut off value of haematocrit indicative of plasma leakage.
  - d. Haematocrit fluctuation of 20% or more
- 4. With regards to assessing the severity of the platelet drop, two secondary endpoints were used:
  - a. The mean nadir platelet count
  - b. The difference in the platelet level between the values of clinic consultation 2 clinic consultation1.
- 5. The difference in the amount of oral fluid intake between the two groups.

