## Severity of haemoconcentration:

#### Haematocrit fluctuation of 20% or more

This was calculated using the following standard formula:

Haematocrit fluctuation = (highest haematocrit – population baseline haematocrit) / population baseline haematocrit X 100%

The average population baseline haematocrit value for a 20 year old adult Malaysian male was 0.45 and for the average 20 year old Malaysian female was 0.38. These average population values were obtained and utilised with kind permission from [name] by personal communication based on her unpublished DENCO study data.

The author will use the average population baseline haematocrit rather than the individual patient's own values because no convalescent sample is routinely done for all the patients enrolled in this pilot study. Moreover, it has been shown by a prior study done in Vietnam which had correctly identified 94% of shocked patients as having capillary leak by utilising the local population mean haematocrit as the baseline for calculating the 20% fluctuation in haematocrit level.

Also, the length of patient follow-up varies from patient to patient depending on the attending doctor's assessment of the patient. This secondary endpoint is chosen as a measure for haemoconcentration based on the previous World Health Organization's guidelines for dengue, which included 20% fluctuation in haematocrit as one of the four diagnostic criteria for dengue haemorrhagic fever (DHF). A local Malaysian study also found a fluctuation of 20% haematocrit level to be highly associated with Dengue Haemorrhagic Fever (using the previous World Health Organization classification system).

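### Unadjusted t tests for peak haematocrit, nadir platelets and the consultation 2 minus 1 changes give up precision that sex and the consultation-1 values would supply at no cost

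*Protocol*

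**What the plan says.** The Statistical analysis section fixes one method for every continuous comparison: "Differences in data between the control and intervention group will be analysed using the Student's t test for continuous variables". It adds that "A p value < 0.05 is considered as statistically significant" and names no covariate or stratification factor.

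Preliminary outcome measures lists the continuous laboratory endpoints this governs: "The mean peak haematocrit" (item 3a), the haematocrit difference between consultations 2 and 1 (3b), the mean nadir platelet count (4a) and the platelet difference between consultations 2 and 1 (4b).

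For the binary endpoint of a 20% haematocrit fluctuation (3d), the protocol uses sex-specific population baselines: "male was 0.45 and for the average 20 year old Malaysian female was 0.38". The plasma-leakage cut-offs for item 3c are also sex-specific, 0.47 for men and 0.40 for women.

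On allocation, Type of randomization says "Simple randomisation will be done, with a 1:1 allocation ratio", and Allocation concealment says "No concealment of allocation will be employed". On size: "The minimum recruited number of participants required for each study group will be 30 patients, giving a minimum number of 60 patients in total".

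Study objectives (objective 3) and Estimated sample size make estimation of the treatment effect, for planning the main trial, a stated purpose of the pilot.

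**The concern.** The protocol treats sex as essential to reading a haematocrit in two of its four haemoconcentration endpoints, then pools men and women in a raw mean for a third. Randomisation is not stratified and the arms may be as small as 30, so the sex mix will often differ between arms. Part of any observed difference in mean peak haematocrit may then be sex mix. Since allocation is not concealed, imbalance need not be due to chance alone.

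Separately, consultation-1 haematocrit and platelets are known before allocation. The screening blood count supplies the platelet result that triggers recruitment, and allocation follows consent. Nadir platelets are nevertheless compared without that starting value, and the two change scores use it in the less efficient way, by subtraction.

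At stake are the precision of the effect estimates, and for peak haematocrit how far one pilot's estimate can be read as an effect of the fluid chart. The same estimates, with their SDs, are meant to inform the main trial.

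**Working it through.** **Inputs from the protocol.** Sex gap in mean haematocrit: 0.45 − 0.38 = 0.07; the cut-offs give the same gap, 0.47 − 0.40 = 0.07. Minimum size: 30 per arm. Simple 1:1 randomisation. No effect size, SD or power is given behind the 30, so there is no sample-size calculation to reproduce beyond 2 × 30 = 60.

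**Assumptions.** 50% men; within-sex SD *s* of peak haematocrit 0.03 to 0.05; the population sex gap carries over to peak values; exactly 30 per arm; correlation *r* between the consultation-1 value and the later value taken over a range; a two-sided test. Consultation 1 is read as the recruitment visit. The text does not name sex as a recorded item, but items 3c and 3d cannot be computed without it.

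**Step 1: variance of peak haematocrit due to sex.** Between-sex variance = 0.5 × 0.5 × 0.07² = 0.001225. Share of total = 0.001225 / (0.001225 + s²). SE = SD × √(2/30). Half-width = 1.96 × SE.

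| s | Total SD | Share due to sex | SE unadjusted | SE adjusted | 95% half-width, unadjusted | 95% half-width, adjusted |
|---|---|---|---|---|---|---|
| 0.03 | 0.046 | 58% | 0.0119 | 0.0077 | 0.023 | 0.015 |
| 0.04 | 0.053 | 43% | 0.0137 | 0.0103 | 0.027 | 0.020 |
| 0.05 | 0.061 | 33% | 0.0158 | 0.0129 | 0.031 | 0.025 |

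To match an adjusted analysis of 60 patients, an unadjusted one would need 60 / (1 − share): about 142, 106 and 89 patients for s = 0.03, 0.04 and 0.05. With 60% or 70% men the share is 29% to 57%.

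**Step 2: chance sex imbalance.** The SD of the between-arm difference in male share is √(2 × 0.25/30) = 0.129, so a typical shift in the mean difference is 0.07 × 0.129 = 0.009. From the exact difference of two binomials with 30 patients each, a gap of at least 3 men (10 points) has probability 52%, and of at least 6 men (20 points) 15.5%. At 60% and 70% men the latter is 14.7% and 12.0%. A 20-point gap shifts the estimate by 0.07 × 0.20 = 0.014, which is 0.9 to 1.2 unadjusted SEs (0.014/0.0158 to 0.014/0.0119).

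**Step 3: behaviour of the t test on peak haematocrit with no treatment effect** (simulation, 40,000 runs per setting, s = 0.03 to 0.05). Averaged over all randomisations, the rejection rate is 5.0%. Given 15 v 15 men it is 0.3% to 1.7%; given 18 v 12, 9% to 11%; given 19 v 11, 17% to 27%.

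**Step 4: the consultation-1 value.** Regression on the starting value multiplies the variance by 1 − r² relative to the raw later value. Relative to the change score the factor is (1 + r)/2, if the variances are equal at the two visits.

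| r (assumed) | Against raw value, 1 − r² | Against change score, (1 + r)/2 |
|---|---|---|
| 0.5 | 0.75 | 0.75 |
| 0.7 | 0.51 | 0.85 |
| 0.8 | 0.36 | 0.90 |

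These factors do not add to the sex gain in step 1. In the haematocrit change a constant sex offset cancels, and the protocol gives no sex difference for platelets.

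**The case against.** The strongest reply is that nothing is wrong with the test. Its standard error already contains the between-sex variation, so its 5% level holds over repeated randomisation. A 20-point imbalance is about one standard error, which the confidence interval is built to cover. This is a feasibility pilot whose aim concerns oral fluid intake; the haematocrit and platelet measures are surrogate or secondary. Covariate adjustment is also often left to an analysis plan, and none is shown.

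The validity point stands, and so does the point about stakes. The last point does not: the protocol names the test for all continuous comparisons, so the lack of adjustment is a stated choice.

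Three stronger readings are tempting, and the protocol does not support them.

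- A reader might infer that the sex gap exceeds any plausible effect of drinking more. The protocol gives no expected haematocrit effect. Also, 0.07 is a gap between individuals; what enters the arm comparison is 0.07 times the imbalance, typically 0.009.
- A reader might infer that the peak haematocrit comparison is dominated by sex mix. Sex exceeds half the variance only towards the lowest assumed SD; at 0.04 and 0.05 it is 43% and 33%.
- A reader might infer that the pooled SD would wrongly inflate the main trial. It is too large only relative to an adjusted main-trial analysis; for an unadjusted one it is the right input. The protocol settles neither that analysis nor which outcome will drive the sample size.

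The baseline gain also rests on softer ground. The correlations are not in the protocol. Platelets at entry are capped at 150 × 10⁹/L, so equal variance at the two visits cannot be taken for granted. The change scores already use consultation 1, so their gain is only 10% of variance at r = 0.8.

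**Conclusion.** The point holds as a free improvement, of minor to moderate importance. The planned t tests are valid on average but inefficient, given information that the study already has before allocation.

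The sex argument is confined to mean peak haematocrit. There, adjustment removes 58% to 33% of the variance if half the patients are men and the within-sex SD is 0.03 to 0.05. It also removes the shift caused by sex imbalance, which reaches 0.014 at a 20-point gap. The direction follows from the protocol's own 0.07 gap; the size depends on assumed values.

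For nadir platelets and the two changes the gain comes only from the consultation-1 value, and its size is unknown until the correlations are seen.

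It would be wrong to conclude that the test has an inflated false-positive rate. The rates in step 3 are conditional on the imbalance that occurs, and they average to 5.0%.

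**What to change.** In Statistical analysis, replace the t test for these endpoints with linear regression. Analyse peak haematocrit, nadir platelets and the consultation-2 haematocrit and platelet values on arm and the consultation-1 value, adding sex for the haematocrit models. Report the adjusted difference between arms with its 95% CI.

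Report both the raw SD and the residual SD. Use the residual SD to plan the main trial only if the main trial will use the same adjusted analysis; otherwise use the raw SD.

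State that consultation 1 is the recruitment visit and that its blood count precedes allocation, and confirm that sex is an item on the data collection form.

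The cost is a few sentences. No new data are needed, clinical care does not change, and SPSS, the package named in the protocol, fits these models.
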